6.3. Missing Data

6.3.1. Missing Efficacy Endpoints

The absence of data related to BTH can only be interpreted to mean that no BTH has occurred. Thus all efficacy data will be analyzed as-is and no imputations will be performed.

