8.1. Primary Efficacy Endpoint and Analysis

The primary efficacy endpoint is the proportion of participants who experience free C5-associated BTH through Day 351.

BTH is defined as at least 1 new or worsening symptom or sign of intravascular hemolysis (fatigue, hemoglobinuria, abdominal pain, shortness of breath [dyspnea], anemia [hemoglobin < 10 g/dL], MAVE, including thrombosis, dysphagia, or erectile dysfunction) in the presence of elevated LDH, which is defined as LDH \geq 2 × ULN. The determination about whether a BTH has occurred will be reflected on the BTH form of the eCRF. In the event of a BTH outside the visit schedule, an unscheduled visit will occur, at which point all information pertaining to the BTH will be collected.

Free C5-associated BTH is defined as BTH concurrent with free C5 concentrations $\geq 0.5 \,\mu\text{g/mL}$. The first C5 concentration captured on or after the date of the BTH will be considered when defining a BTH event as free C5-associated.

The proportion of participants who experience free C5-associated BTH through Day 351 will be calculated along with a 2-sided exact 95% CI using the Clopper-Pearson method. All data will be listed.

Participants who withdraw from the study due to lack of efficacy during the Evaluation Period will be considered as non-responders and will be counted in the group with free C5 associated BTH if free C5 is ≥ 0.5 µg/mL at ET visit. For participants who withdraw from the study for any other reason during the Evaluation Period, their data up to the time of withdrawal will be used to assess free C5 associated BTH.

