8.2. Secondary Efficacy Endpoints and Analyses

8.2.1. Proportion of participants with BTH

The proportion of participants who experience BTH through Day 351 will be summarized along with a 2-sided 95% exact CI using the Clopper-Pearson method.

The determination about whether a BTH has occurred will be reflected on the BTH form of the eCRF. In the event of a BTH outside the visit schedule, an unscheduled visit will occur, at which point all information pertaining to the BTH will be collected.

All data will be listed.

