8.2.3. Proportion of participants with transfusion

Proportion of participants receiving a transfusion from baseline to Day 351 will be summarized along with a 2-sided 95% exact CI using the Clopper-Pearson method. Number of transfusion episodes, number of units transfused will also be summarized for participants receiving transfusions.

Participants who withdraw from the study due to lack of efficacy during the Evaluation Period will be considered as non-responders and will be counted in the group receiving transfusion. For participants who withdraw from the study for any other reason during the Evaluation Period, their data up to the time of withdrawal will be used to assess the proportion of participants receiving a transfusion.

All data will be listed.

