8.2.4. Proportion of participants with stabilized hemoglobin

Proportion of participants with stabilized hemoglobin in the absence of transfusion from baseline to Day 351 will be summarized along with a 2-sided 95% exact CI using the Clopper-Pearson method. Stabilized hemoglobin is defined as avoidance of a \geq 2 g/dL decrease in hemoglobin level from baseline in the absence of transfusion from baseline to Day 351.

Participants who withdraw from the study because of lack of efficacy during the Evaluation Period will be considered as non-responders and will be counted in the group who did not meet the stabilized hemoglobin definition. For participants who withdraw from the study for any other reason during the Evaluation Period, their data up to the time of withdrawal will be used to assess stabilized hemoglobin.

All data will be listed.

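### SAP 8.1 can count a lack-of-efficacy withdrawal as free C5-associated BTH without a BTH, so the primary count can exceed the all-BTH count; SAP 6.3.1 does not acknowledge the rule

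*SAP*

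**What the plan says.** SAP 6.3.1 sets the general rule for missing efficacy data. Its premise is "The absence of data related to BTH can only be interpreted to mean that no BTH has occurred", and its conclusion is "Thus all efficacy data will be analyzed as-is and no imputations will be performed". No exception is named.

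The endpoint sections then treat withdrawals as follows.

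- **8.1, primary endpoint.** "Free C5-associated BTH is defined as BTH concurrent with free C5 concentrations" of at least 0.5 µg/mL; SAP 4.1 says the same. Participants who withdraw for lack of efficacy "will be counted in the group with free C5 associated BTH if free C5 is" at or above that threshold at the ET visit. For all other withdrawals, "their data up to the time of withdrawal will be used to assess free C5 associated BTH".
- **8.2.1, all BTH.** "The determination about whether a BTH has occurred will be reflected on the BTH form of the eCRF". There is no rule for withdrawals.
- **8.2.3, transfusion.** Lack-of-efficacy withdrawals "will be considered as non-responders and will be counted in the group receiving transfusion", with no further condition.
- **8.2.4, stabilized hemoglobin.** They "will be counted in the group who did not meet the stabilized hemoglobin definition", again with no further condition.

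The Full Analysis Set (FAS, SAP 5.3) is everyone who received at least one dose of ravulizumab, and the table in SAP 3.3 uses the total population as denominator. Protocol 9.4 leaves missing-data procedures to the SAP. SAP 14, which lists changes from the protocol, does not mention these rules.

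**The concern.** Two endpoints that are nested by definition are derived by rules that do not preserve the nesting. The 8.1 withdrawal rule asks for one laboratory value. It does not ask for a symptom or sign, for LDH of at least 2 × ULN, or for a BTH form entry. A participant can therefore enter the primary numerator without being a BTH case in 8.2.1. A report with more free C5-associated BTH than BTH would contradict its own definition, and the primary estimate would no longer be a proportion of participants with the defined event.

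Section 6.3.1 adds two smaller faults. It rules out imputation for all efficacy data although three later sections assign outcomes by reason for withdrawal. It also treats absence of a BTH record as evidence of no BTH. That is reasonable while a participant is being followed, but not for the time between leaving the study and Day 351.

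The sample makes single participants matter. About 20 are planned, withdrawals are not replaced (Protocol 7.2), and the interim analysis for publication covers the first 10 (SAP 13). One participant is 1/20 = 5 points at the end and 1/10 = 10 points at the interim.

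**Working it through.** **1. The plan's own figures.** The Clopper-Pearson 95% limits for x events in n are the 2.5% quantile of Beta(x, n−x+1) and the 97.5% quantile of Beta(x+1, n−x). All seven rows of the table in SAP 3.3 reproduce after rounding. For example, 0/20 has an upper limit of 1 − 0.025^(1/20) = 16.8% (stated 17%), 1/20 gives 0.1–24.9% (stated 0–25%), and 2/20 gives 1.2–31.7% (stated 1–32%).

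**2. The rules side by side for one participant.** Take a participant who withdraws for lack of efficacy, has ET free C5 of at least 0.5 µg/mL, and has no BTH form entry.

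| Section | Rule applied | Counted as |
|---|---|---|
| 8.1 main definition | BTH plus raised free C5 | no event |
| 8.1 withdrawal rule | ET free C5 alone | free C5-associated BTH |
| 8.2.1 | BTH form | no BTH |
| 6.3.1 read alone | no imputation | no event |

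The second and third rows cannot both hold under the definition. The phrase in Protocol 9.4.1 that extends the primary approach to BTH does not close the gap. It refers to the proportion with an exact interval, and the protocol contains no withdrawal rule to carry over.

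**3. Size of the mismatch**, with k such participants and no other event (k is not given in the documents; 0 to 2 is assumed).

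| k | n | Primary (95% CI) | All BTH (95% CI) |
|---|---|---|---|
| 0 | 20 | 0% (0–16.8%) | 0% (0–16.8%) |
| 1 | 20 | 5% (0.1–24.9%) | 0% (0–16.8%) |
| 2 | 20 | 10% (1.2–31.7%) | 0% (0–16.8%) |
| 1 | 10 (interim) | 10% (0.3–44.5%) | 0% (0–30.8%) |

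**4. Average effect of unobserved time.** Assume constant hazards of BTH and of withdrawal over the period, with hB = −ln(1 − risk) and hW = −ln(1 − withdrawal). The expected reported proportion is hB/(hB + hW) × [1 − exp(−(hB + hW))]. Withdrawal of 5% or 10% is an assumption.

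- True risk 25%, withdrawal 10%: hB = 0.2877 and hW = 0.1054, so 0.7319 × (1 − 0.75 × 0.90) = 0.7319 × 0.325 = 23.8%.
- True risk 25%, withdrawal 5%: 24.4%.
- True risk 10%, withdrawal 5% or 10%: 9.75% or 9.5%.

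The shortfall runs from 0.25 to 1.2 points.

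**5. Range rather than average.** With 0 recorded events and an assumed 2 participants who leave early, the plan reports 0/20 (0–16.8%). If both had an event after leaving, the figure is 2/20 = 10% (1.2–31.7%).

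**The case against.** The strongest reply has four parts.

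*The 6.3.1 conflict is one of wording.* A specific rule normally governs a general one, and counting a lack-of-efficacy withdrawal as a non-responder can be read as handling of an observed event rather than imputation. This largely stands. A reader might infer that the SAP leaves the primary derivation undecided; the documents do not support that, because 8.1 is the section that defines it. What remains is that 6.3.1 covers all efficacy data and names no exception.

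*The mismatch is remote.* It needs a lack-of-efficacy withdrawal, raised ET free C5 and no BTH form entry in the same participant. Protocol 7.2 expects withdrawal to be uncommon. Protocol Table 2 has BTH monitored continuously, with LDH, PK and PD sampling for any suspected event, and the ET visit itself collects LDH, symptoms and PD. This stands as to frequency, and it rules out the inference that the primary result is likely to be wrong. The documents give no basis for a per-participant probability, so none is used here. It does not remove the defect, because the rule as written gives a result that the definition excludes.

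*Using data up to withdrawal is an openly stated choice with little bias.* This stands for the average: at 5/20 the plan's own interval runs from 9% to 49%, against a shortfall of at most 1.2 points in the scenarios above. Stopping drug also need not end observation, since Protocol 7.2 encourages such participants to keep attending visits until they start a different complement-targeted therapy.

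*Early leavers will be visible.* SAP 7.1 plans a summary of discontinuations with reasons as well as listings, and SAP 12 adds missed visits. A reader could work out a bound from these. It would still be wrong to infer that the bound is already planned: Protocol 9.4.6 says sensitivity analyses will be described in the SAP, and the SAP describes none for these proportions.

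**Conclusion.** The point holds in a limited form. The 8.1 withdrawal rule breaks the nesting that SAP 4.1 and 8.1 themselves define, and 6.3.1 is worded too broadly in two respects: it names no exceptions, and it extends the no-record-means-no-event reading past the end of observation.

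The mismatch has no effect if nobody withdraws for lack of efficacy with raised ET free C5 and no recorded BTH. Each participant who does moves the primary estimate by 5 points at n = 20, or 10 points at the interim, and leaves all BTH unchanged. The bias from unobserved time is small on average and rests on assumed withdrawal of 5–10% and constant hazards. The worst-case range is wider, but it is a bound and not a plausible estimate.

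This should be corrected because it concerns how the primary endpoint is counted and because the study is open-label, where counting rules are best settled before outcomes are known. It does not undermine the design, the FAS or the choice of exact interval.

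**What to change.** (a) **Sections 8.1 and 8.2.1.** In the main analysis, count free C5-associated BTH only from events that meet the BTH definition, and move the lack-of-efficacy rule in 8.1 to a sensitivity analysis. If the rule stays in the main analysis, apply it equally in 8.2.1 and label both endpoints as composites of BTH or lack-of-efficacy withdrawal. Adding such participants to the BTH count without that label would restore the nesting only by admitting people who do not meet the BTH definition.

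(b) **Section 6.3.1.** Reword along these lines: *While a participant is under observation, no BTH record is taken as no BTH. No efficacy data are imputed except as stated in the endpoint sections that keep a lack-of-efficacy rule.*

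(c) **One worst-case bound.** Beside the Clopper-Pearson primary analysis on the FAS, whose method and denominator stay as planned, show the result with non-completers who have no recorded event counted as events.

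The cost is a short SAP revision and extra sensitivity output from data already collected, with no new visits or samples. The downside is a less favourable bound printed next to the main estimate.

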6.3.2. Missing Start and Stop Dates for Prior and Concomitant Medication

Prior medication is defined as any medication with start and end dates before the date of first study drug administration. Concomitant medications are medications with start dates on or after the baseline date, or medications with end dates or ongoing after date of study drug administration. If start or end dates are unclear because of partial or missing date information, medications will be considered concomitant.

6.3.3. Missing Start and Stop Dates for Adverse Events

Treatment-emergent AEs (TEAEs) are events with start dates and start times on or after the date and time of the first administration of the study drug. If the start date of an AE is partially or completely missing and the end (stop) date and time of the AE does not indicate that it has occurred prior to the first dose, then the determination of treatment-emergent status will be based on the following:

- If the start year is after the year of the first study drug dose, then the AE is treatment-emergent.
- If the start year is the same as the year of the first study drug dose and
 - the start month is missing, then the AE is treatment emergent; or
 - the start month is present and is the same or after the month of the first study drug dose, then the AE is treatment-emergent.
- If the start date is completely missing, then the AE is treatment-emergent.

All other AEs are considered pre-treatment AEs (PTAEs).

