#### 2.3.1. Risk Assessment

Risks of Clinical Significance	Summary of Data/ Rationale for Risk	Mitigation Strategy
Potential Risks		
Serious hemolysis after drug discontinuation	This potential disease-associated risk is based on a theoretical possibility, associated with abrupt ravulizumab discontinuation, resulting in a so- called rebound effect. Rebound effect is described for many biologicals but has not been observed in ravulizumab clinical trials.	The effects are most likely not completely preventable, but their severity can be minimized by avoiding abrupt drug discontinuation. Participants who discontinue the drug will be followed up for 16 weeks if participants remain in the study.
Serious infection	This potential risk is a based on the mode of action of ravulizumab and experience with the use of eculizumab. Since the relevance of serious infection with ravulizumab therapy has not been confirmed in clinical trials, this remains a potential risk.	Increased awareness of healthcare professionals and participant about the potential risk of serious Infection. Monitoring for signs and symptoms of serious infections will be conducted as part of routine safety assessments for this study.
Malignancies and hematologic abnormalities	The natural evolution of PNH disease makes PNH patients more prone to development of hematologic abnormalities or malignancies as approximately 30-70% of PNH patients eventually develop aplastic anemia or myelodysplastic syndrome. The potential role of ravulizumab in the risk of such abnormalities or malignancies (if any) is unknown	Monitoring as part of routine safety assessments for this study.
Immunogenicity	Treatment with any therapeutic protein has the potential to induce an immune response. Potential clinical consequences may include severe hypersensitivity type reactions, decrease in efficacy and induction of autoimmunity, including antibodies to the endogenous form of the protein (Casadevall, 2002; Li, 2001). Protein therapies administered IV have the potential risk of causing local (infusion-site reactions) and systemic reactions (infusion-associated reactions).	In the ALXN1210-PNH-103 and ALXN1210-PNH-201 studies, no participants have returned a positive ADA sample. ADA will be assessed. Monitoring for infusion reactions will be conducted as part of routine safety assessments for this study.

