16.2.5.3. Listing Conventions

- Listings will be sorted for presentation in order of participant number, visit/collection day, and visit/collection time.
- Dates will be printed in SAS DATE9.format ('DD_MMM_YYYY': 01JUL2000). Missing portions of dates will be represented on participant listings as dashes (-JUL2000).
- All observed time values will be presented using a 24-hour clock HH:MM or HH:MM:SS format (eg, 11:26:45, or 11:26). Time will only be reported if it was measured as part of the study.
- Units will be included where available.

This document is confidential

SAP Version: 2.0 09-Feb-2023

Controlled Document ID: 3903A.02, Effective Date 31-Aug-2020

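### SAP 6.3.3 has no rule for an adverse event dated to the first-dose day without a usable clock time, and its residual sentence makes that event pre-treatment, in conflict with SAP 11.1 and Protocol 9.4.2.1

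*SAP*

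**What the plan says.** SAP 6.3.3 opens with its main definition: TEAEs are "events with start dates and start times on or after the date and time of the first administration of the study drug". A set of fallback rules follows, introduced by the condition "If the start date of an AE is partially or completely missing", provided that the stop date and time do not place the event before the first dose.

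Within the year of first dose, a start date that lacks its month gives a TEAE. Where the month is known, the fallback rule reads: "the start month is present and is the same or after the month of the first study drug dose, then the AE is treatment-emergent".

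A start year after the dosing year, or a wholly missing start date, also gives a TEAE. The section closes with "All other AEs are considered pre-treatment AEs (PTAEs").

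Two other places define the same term. Protocol 9.4.2.1 uses onset from the first ravulizumab dose onward. SAP 11.1 uses onset from the first administration onward, and adds earlier events that become more frequent or more severe afterwards. Neither mentions a clock time. SAP 11.1 then also classes everything else as PTAE. SAP 14, which lists changes from the protocol analysis, does not mention a start-time requirement.

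**The concern.** On the dosing day, and only on that day, the calendar date cannot settle whether an event began before or after the infusion. The main definition in SAP 6.3.3 relies on a clock time for this, and the section gives no instruction for when the time is absent. The residual sentence then supplies an answer by default, and that answer is pre-treatment.

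Two things make this look like an oversight. Less information gives the opposite class: an event known only to have begun in the dosing month is a TEAE, and so is one with no date at all. The SAP also resolves doubt in the cautious direction elsewhere. Medications with unclear dates become concomitant (6.3.2), missing relationship becomes related, and missing severity becomes Grade 3 (11.1).

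The stake is the safety objective. Protocol 2.3.1 lists infusion-associated and hypersensitivity-type reactions under immunogenicity and states: "Monitoring for infusion reactions will be conducted as part of routine safety assessments for this study". Day 1 is the first ravulizumab infusion. An untimed reaction dated to that day could be missing from the TEAE, related-TEAE and grade tables, and from the listing of TEAEs leading to withdrawal of study drug.

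**Working it through.** The documents give no figure for this point, so the check is a trace of the rule. Each onset pattern was classified by the literal text of SAP 6.3.3. Complete dates were also classified by a calendar-date reading of SAP 11.1 and Protocol 9.4.2.1. The first dose is set for illustration at 15 June 2021, 10:00.

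| Recorded onset | SAP 6.3.3, literal | SAP 11.1 / Protocol 9.4.2.1, by date |
|---|---|---|
| Day 1, 12:00 | TEAE (main definition) | TEAE |
| Day 1, 08:00 | PTAE (residual) | TEAE |
| **Day 1, no time** | **PTAE (residual)** | **TEAE** |
| Day 2, no time | TEAE (main definition) | TEAE |
| Day -1, no time | PTAE (residual) | PTAE |
| June 2021, day missing | TEAE (fallback) | not applicable |
| 2021 only | TEAE (fallback) | not applicable |
| No date at all | TEAE (fallback) | not applicable |
| May 2021, day missing | PTAE (residual) | not applicable |
| 2020 only | PTAE (residual) | not applicable |
| 15 June, year missing | PTAE (residual) | not applicable |

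The bold row is the gap. Its neighbours show how narrow it is: a Day 2 or Day -1 event needs no time, because any clock time on those dates gives the same class.

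**Can the gap occur?** The comparison needs two times.
- *Event onset time.* Protocol 8.3.1 and Appendix 3 (Section 10.3) do not ask for it. SAP 16.2.5.3 is conditional: "Time will only be reported if it was measured as part of the study".
- *Dose time.* Protocol 6.4 commits to recording it for doses given in the clinic. The administration note in Protocol Table 2 also allows dosing at home or at a nearby facility and does not exclude Day 1. Without a dose time, even a timed Day 1 event cannot meet the main definition.

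**Size.** The inputs are the planned 20 participants (SAP 3.3) and the 10-participant interim (SAP 13), which includes all outputs. SAP 11.1 counts a participant once per category, so a participant's count changes only if the untimed Day 1 event is that person's sole TEAE in the category.
- Final analysis: 1/20 = 5 points per such participant.
- Interim: 1/10 = 10 points per such participant.
- Assumed range of 0, 1, 2 or 3 such participants at n=20: 0/20 = 0, 1/20 = 5, 2/20 = 10 and 3/20 = 15 points.

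For one preferred term with no other reports, two such participants would change the TEAE row from 2/20 (10%) to 0/20. The documents give no count, so this range shows scale only and is not an estimate.

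**The case against.** The best defence is that the SAP does not settle on pre-treatment at all. SAP 11.1 is the section that governs the adverse event tables, and it requires no clock time. An infusion reaction by its nature begins during or after the infusion, so it meets SAP 11.1 and Protocol 9.4.2.1 whether or not a time was written down. Also, SAP 6.3.3 speaks of start times and stop times, which suggests that the case report form collects them. Misclassified events would still be seen, because PTAEs have their own table and listing.

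Much of this stands. It makes the problem a conflict between definitions plus an unhandled case, and it leaves the frequency open. It does not remove the problem. SAP 6.3.3 is where a programmer looks for missing onset information, and its literal result differs from that of SAP 11.1. Collecting a time field is also not the same as having it filled in for every event.

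Several stronger readings are tempting but unsupported:
- *That unresolved onsets generally go to PTAE.* The fallback rules send most partial dates, and a wholly missing one, to TEAE.
- *That the event is counted against eculizumab and both tables tilt towards ravulizumab.* Participants do receive eculizumab during Screening, but the SAP's category is only pre-treatment, and no comparison of TEAEs with PTAEs is planned.
- *That Day 1 is the likeliest day for a reaction.* The protocol names the risk without singling out a day.
- *That every affected participant moves a rate by 5 points.* The once-per-category rule prevents this when the participant has another TEAE in the category.

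**Conclusion.** The point holds as a specific gap. For an event dated to the first-dose day with no usable clock time, the literal text of SAP 6.3.3 gives PTAE. That is the anti-conservative class. It is out of line with the section's treatment of vaguer dates and with the SAP's other missing-data defaults, and it conflicts with a date-level reading of SAP 11.1 and Protocol 9.4.2.1.

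The effect is 5 points per participant at n=20, or 10 points in the interim, for a category in which the event is that participant's only TEAE. Otherwise that category's participant count does not change. The total effect cannot be estimated, because the documents do not say whether onset time is collected. If it is always recorded along with the dose time, the effect is nil; if it is never collected, every Day 1 event is exposed. The clarification should be made because it is cheap and the interim is intended for publication.

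A related mismatch belongs with it: the worsening clause in SAP 11.1 is absent from SAP 6.3.3.

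**What to change.** Add to SAP 6.3.3: *An AE that starts on the date of first dose, with its start time or the dose time missing, is treatment-emergent unless the available start or stop information shows that it began before the first infusion.*

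Then use one TEAE definition in SAP 6.3.3 and 11.1, including the worsening clause, and reverse the residual sentence: *An AE is a PTAE only if onset before the first dose is documented and the event did not worsen in frequency or severity afterwards.*

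This is better than a pure calendar-date rule, which would also turn a timed pre-dose Day 1 event into a TEAE. Under the wording above, that event stays a PTAE unless it worsened, and untimed Day -1 and Day 2 events keep their class. The case with only the year missing becomes a TEAE unless the stop date shows otherwise.

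The cost is a few sentences and a small change to the classification program. The downside is that a few true pre-dose Day 1 events may be counted as TEAEs.
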